7.1.5.2 Post-treatment follow-up

All patients who discontinued treatment during the treatment phase for reasons other than death, lost to follow-up, pregnancy or PD (radiological as assessed by investigator) ([Section 7.1.3](#)) will continue tumor assessments as per [Table 7-1](#) (every 8 weeks) thereafter until PD (radiological as assessed by investigator), withdrawal of consent from tumor assessment, lost to follow-up or death. Once the patient ceases tumor follow-up, the reason for completion should be recorded on the End of Post Treatment Phase Disposition eCRF page.

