15.1.25 Definition of start and end dates for time to event variables

Assessment date

For each assessment (i.e. evaluation number), the **assessment date** is calculated as the latest of all measurement dates (e.g. X-ray, CT-scan) if the overall lesion response at that assessment is CR/PR/SD/UNK. Otherwise - if overall lesion response is progression - the assessment date is calculated as the earliest date of all measurement dates at that evaluation number.

Start dates

For all “time to event” variables, other than duration of response, the randomization/ date of treatment start will be used as the start date.

For the calculation of duration of response the following start date should be used:

- Date of first documented response is the assessment date of the first overall lesion response of CR (for duration of overall complete response) or CR / PR (for duration of overall response) respectively, when this status is later confirmed.

End dates

The end dates which are used to calculate ‘time to event’ variables are defined as follows:

- Date of death (during treatment as recorded on the treatment completion page or during follow-up as recorded on the study evaluation completion page or the survival follow-up page).
- Date of progression is the first assessment date at which the overall lesion response was recorded as progressive disease.
- Date of last adequate tumor assessment is the date the last tumor assessment with overall lesion response of CR, PR or SD which was made before an event or a censoring reason occurred. In this case the last tumor evaluation date at that assessment is used. If no post-baseline assessments are available (before an event or a censoring reason occurred) the date of randomization/start of treatment is used.
- Date of next scheduled assessment is the date of the last adequate tumor assessment plus the protocol specified time interval for assessments. This date may be used if back-dating is considered when the event occurred beyond the acceptable time window for the next tumor assessment as per protocol (see [Section 15.1.26](#)).

Example (if protocol defined schedule of assessments is 3 months): tumor assessments at baseline - 3 months - 6 months - missing - missing - PD. Date of next scheduled assessment would then correspond to 9 months.

Date of discontinuation is the date of the end of treatment visit.

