15.1.39 Censoring reason

In order to summarize the various reasons for censoring, the following categories will be calculated for each time to event variable based on the treatment completion page, the study evaluation completion page and the survival page.

For survival the following censoring reasons are possible:

- Alive
- Lost to follow-up

For PFS and TTP (and therefore duration of responses) the following censoring reasons are possible:

- Ongoing without event
- Lost to follow-up
- Withdraw consent
- Adequate assessment no longer available*
- Event documented after two or more missing tumor assessments (optional, see [Table 15-5](#))
- Death due to reason other than underlying cancer (*only used for TTP and duration of response*)
- Initiation of new anti-cancer therapy

*Adequate assessment is defined in [Section 15.1.25](#). This reason is applicable when adequate evaluations are missing for a specified period prior to data cut-off (or prior to any other censoring reason) corresponding to the unavailability of two or more planned tumor assessments prior to the cut-off date. The following clarifications concerning this reason should also be noted:

- This may be when there has been a definite decision to stop evaluation (e.g. reason="Sponsor decision" on study evaluation completion page), when patients are not followed for progression after treatment completion or when only UNK assessments are available just prior to data cut-off).
- The reason "Adequate assessment no longer available" also prevails in situations when another censoring reason (e.g. withdrawal of consent, loss to follow-up or alternative anti-cancer therapy) has occurred more than the specified period following the last adequate assessment.
- This reason will also be used to censor in case of no baseline assessment.

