If a patient has not progressed or is not known to have died at the date of analysis cut-off or has received any further anticancer therapy in the absence of disease progression, PFS will be censored at the date of last adequate tumor assessment before the earlier of the cut-off date or the start date of new anticancer therapy. Clinical deterioration will not be considered as a qualifying event for progression. Refer to [Table 2-2](#) for censoring and event date options and outcomes for PFS.

In particular, PFS will be censored at the last adequate tumor assessment if one of the following occurs: absence of event; the event occurred after a new anticancer therapy is given; the event occurred after two or more missing tumor assessments (see [Section 4.7.1](#)). See also [Section 4.6.1](#) describing the special case of a missing baseline tumor assessment.

PFS will be described in tabular and graphical format using Kaplan-Meier methods as described for DOR, including estimated median (in months) with 95% CI, 25th and 75th percentiles with 95% CIs, and Kaplan-Meier estimated probabilities with corresponding 95% CIs at several time points (including at least 4, 8, 12, 15 and 18 months). Censoring reasons will also be summarized.

In addition, the supportive analysis of PFS with censoring rule modified by ignoring further anticancer therapy ('F' in [Table 2-2](#)) will be considered when the percentage of patients censored due to the initiation of new anticancer therapy in the main analysis (for censoring reason classification, see [Section 4.7.1](#)) is equal to or more than 25% of the FAS (i.e., ≥ 5 out of 20 patients). In this supportive analysis, data from tumor assessments performed after the start of further anticancer therapy will also contribute to the determination of censoring and event date for PFS. Except for further anticancer therapy, the same censoring rule used for the main analysis will be followed. PFS will be described in a similar way, as needed.

Overall survival

Overall survival (OS) is defined as the time from the start date of study drug to the date of death due to any cause. If a patient is alive at the date of the analysis cut-off or lost to follow-

up, OS will be censored at the last contact date prior to the cut-off date (see [Section 4.3](#) for further details on derivation of last contact date).

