As detailed in Section 15 (Appendix 2) of the protocol, the PFS censoring and event date options depend on the presence and the number of missing tumor assessments. *For example, an event occurring after two or more missing assessments is censored in the analysis of PFS at the last adequate tumor assessment before the event date.*

An exact rule to determine whether there is none, one or two missing assessments is therefore needed. This rule will be based on the distance between the last adequate tumor assessment date and the event date.

If the distance is larger than threshold D_1 or D_2 then the analysis will assume one or two missing assessments, respectively. The threshold D_1 will be defined as the protocol specified interval between the tumor assessments plus the protocol allowed window around the assessments. Similarly, the threshold D_2 is defined as two times the protocol specified interval between the tumor assessments plus the protocol allowed window around the assessments. In this study, the protocol defined schedule of tumor assessment is every 8 weeks and each assessment is expected to be performed at the scheduled time point plus or minus 1 week, i.e., the window is 2 weeks, then any distance larger than $D_1 = 8 + 2 = 10$ weeks means one missing assessment and any distance larger than $D_2 = (8 \times 2) + 2 = 18$ weeks means two missing assessments.

The same definition of D_2 will be used to determine the PFS censoring reason.

Possible censoring reasons for PFS are:

1. Ongoing without event
2. Lost to follow-up
3. Withdraw consent
4. Adequate assessment no longer available
5. New cancer therapy added prior to disease progression
6. Event after ≥ 2 missing tumor assessments

PFS censoring reason is then derived by the following sequence of rules.

- If patient is considered to have a PFS event then PFS censoring reason is set to missing.
- Else if patient has had no baseline tumor assessment then PFS censoring reason = 4.
- Else if start date of new anti-neoplastic therapy is before any PFS event which is less than D_2 distance after date of last adequate tumor assessment (LATA), i.e., if $(\text{PFS event date} - \text{LATA date}) \leq D_2$, then PFS censoring reason = 5.
- Else if patient has a PFS event after two or more missing assessments, i.e., if $(\text{PFS event date} - \text{LATA date}) > D_2$ and PFS event is before min date, then PFS censoring reason = 6.

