- Else if min date = date of withdrawal of consent and $(\text{date of withdrawal of consent} - \text{LATA date}) \leq D_2$ then PFS censoring reason = 3.

- Else if min date = date of treatment discontinuation and (date of treatment discontinuation – LATA date \leq D₂) and date of discontinuation reason in the [End of Treatment Phase Disposition] eCRF page = ‘Lost to follow-up’ then PFS censoring reason = 2.
- Else if min date = analysis cut-off date and (analysis cut-off date – LATA date \leq D₂) then PFS censoring reason = 1.
- Else PFS censoring reason = 4.

where min date = minimum of non-missing (analysis cut-off date, start date of further anti-neoplastic therapy, date of withdrawal of consent, date of discontinuation due to loss to follow-up).

Non-measurable disease at baseline

As specified in Section 15 (Appendix 2) of the protocol, the RECIST 1.1 criteria imply that only patients with measurable disease at baseline should be included in the study. If a patient without measurable disease is enrolled, the intent-to-treat (ITT) principle requires including these patients in the analyses. Hence, analyses will be based on the FAS including patients with either measurable or non-measurable disease. Therefore, a rule needs to be specified on how to handle these cases.

As specified in Section 15 (Appendix 2) of the protocol, overall lesion response can be derived for patients without measurable disease at baseline as follows ([Table 4-2](#)).

Table 4-2 Overall lesion response at each assessment: patients with non-target disease only

Non-target lesions	New lesions	Overall lesion response
CR	No	CR
Non-CR/Non-PD *	No	Non-CR/Non-PD
UNK	No	UNK
PD	Yes or No	PD
Any	Yes	PD

* In general, the Non-CR/Non-PD response for these patients is considered equivalent to an SD response in endpoint determination.

Missing baseline tumor assessment

As specified in Section 15 (Appendix 2) of the protocol, since the timing of PD cannot be determined for patients with missing baseline tumor assessment, these patients are censored in the PFS analysis at the start date of study drug. This rule, however, only applies to the ‘PD component’ of the PFS or DOR assessment.

Patients without baseline tumor assessment who die within D₂ distance from start date of study drug will be counted as having an event in the primary analysis of PFS. All deaths will be counted in the OS analysis regardless of presence or absence of the baseline tumor assessment.

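### SAP 4.7.1 tests the PFS event date instead of the new-therapy start date, so patients censored for new therapy can be coded as lacking adequate assessments

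*SAP*

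**What the plan says.** SAP 4.7.1 derives the PFS censoring reason by an ordered list of rules. After removing patients with a PFS event and those with no baseline assessment, it assigns reason 5 (new therapy) if the "start date of new anti-neoplastic therapy is before any PFS event which is less than" D2 after LATA. The line restates this as PFS event date minus LATA date no greater than D2. D2 is 18 weeks.

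The remaining lines are:

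- Reason 6: a PFS event more than D2 after LATA and before min date.
- Reasons 3, 2 and 1: min date is the withdrawal, loss-to-follow-up or cut-off date respectively, and that date is within D2 of LATA.
- The list ends: "Else PFS censoring reason = 4".

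Min date is the earliest of cut-off, new-therapy start, withdrawal of consent and loss to follow-up. No line tests whether min date is the new-therapy start.

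Protocol 15.1.25 defines LATA as the last CR, PR or SD assessment "which was made before an event or a censoring reason occurred". Protocol 15.1.39 describes reason 4 as a gap "corresponding to the unavailability of two or more planned tumor assessments prior to the cut-off date". It lets reason 4 prevail over another reason, alternative therapy included, when that reason "has occurred more than the specified period following the last adequate assessment".

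SAP 2.8.1 promises a summary of PFS censoring reasons. It also says a supportive PFS analysis that ignores new therapy will be considered when the share of patients censored for new therapy "is equal to or more than 25% of the FAS", given as 5 or more of 20, and it refers to 4.7.1 for the classification. In that analysis "data from tumor assessments performed after the start of further anticancer therapy will also contribute". SAP Section 3 declares no changes from the protocol analyses.

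**The concern.** Reasons 1 to 3 each ask whether the censoring reason itself fell within D2 of LATA, as Protocol 15.1.39 does. Reason 5 alone asks about a different date, that of a later PFS event. Patients censored for new therapy who have no later event, or a late one, therefore fall through to reason 4.

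Two outputs are at stake. The censoring-reason table would report unavailable assessments for patients who missed none. The reason 5 count that decides whether the supportive PFS analysis is considered would be too low, and the patients dropped from it are among those that analysis is meant to examine.

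**Working it through.** **The plan's own figures.** With scans every 8 weeks and a 2-week window (SAP 4.7.1), D1 = 8 + 2 = 10 weeks and D2 = (8 × 2) + 2 = 18 weeks. The trigger is 0.25 × 20 = 5 patients. All reproduce.

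**Running the rules.** Times are weeks from first dose, with LATA at week 8. The corrected rule gives reason 5 when min date is the therapy start and therapy start minus LATA is at most 18.

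| Case | New therapy | Later course | Therapy − LATA | Event − LATA | SAP code | Corrected |
|---|---|---|---|---|---|---|
| A | 12 | SD at 16 and 24, cut-off 24 | 4 | none | 4 | 5 |
| B | 12 | SD at 16 and 24, PD at 32 | 4 | 24 | 4 | 5 |
| C | 12 | PD at 16 or 24 | 4 | 8 or 16 | 5 | 5 |
| D | 30 | any | 22 | over 22 or none | 4 | 4 |

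- Case A has no PFS event date, so reasons 5 and 6 fail. Min date is week 12, the therapy start, so reasons 3, 2 and 1 fail, although cut-off is only 24 − 8 = 16 weeks after LATA. The code is 4.
- Case B fails reason 5 because 32 − 8 = 24 > 18. It fails reason 6 because week 32 is not before min date (week 12). The code is 4.
- Neither A nor B missed a scan.
- Case D is what Protocol 15.1.39 means reason 4 to catch: the therapy starts 22 weeks after LATA. Both rules agree.

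On a weekly grid (therapy 1 to 30 weeks after LATA; event absent or at 1 to 60 weeks; cut-off up to 60 weeks), every disagreement was a corrected 5 coded 4 by the SAP. None went the other way, so the error runs downward only.

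**Effect on the trigger, no rate assumed.** At a true count of 5, one miscoded patient gives 4/20 = 20% and the trigger is missed. At a true count of 6, two miscoded patients do the same.

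**Effect on the trigger, assumed rates.** Let k be the true number censored for new therapy and q the share of them with an event within 18 weeks of LATA. The documents give neither. The chance that the SAP count reaches 5 is P(Bin(k, q) ≥ 5):

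| k | q = 20% | q = 50% | q = 80% |
|---|---|---|---|
| 5 | 0.03% | 3% | 33% |
| 6 | 0.2% | 11% | 66% |
| 8 | 1% | 36% | 94% |

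**Illustrative q.** Take the PFS medians of 3.0 and 7.7 months quoted in Protocol 1.1.3 (another population). At 30.4375 days per month these are 13.05 and 33.48 weeks. Assume exponential times and therapy begun g = 4 or 8 weeks after LATA, so q = 1 − exp(−ln 2 × (18 − g)/median):

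- Median 3.0 months: 52.5% (g = 4) and 41.2% (g = 8).
- Median 7.7 months: 25.2% (g = 4) and 18.7% (g = 8).
- If PD is found only at 8-weekly scans, 16 replaces 18: 47.1%, 34.6%, 22.0% and 15.3% in the same order.

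Patients who switch because treatment is failing may have a higher q.

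**Effect on the supportive analysis.** If scans continue after new therapy, that analysis moves A from censored at week 8 to censored at week 24, and B from censored at week 8 to an event at week 32. Neither counts toward running it. If scans stop, both stay censored at week 8 in either analysis.

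**The case against.** **New-therapy censoring may mean a displaced event.** One sentence in SAP 2.8.1 lists absence of an event separately from an event occurring after new therapy. Reason 5 could then be meant only for patients whose event was displaced by therapy, and case A would not belong in the trigger count. But the same section also describes censoring for patients who receive further therapy without progression, which is case A. Even on the narrower reading, code 4 is wrong for a patient with no missed scan.

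**LATA may mean the scan before the event.** SAP 4.7.1 introduces its distance rule in those terms. In case B that scan is at week 24, PD is 8 weeks later and the code is 5. This reading is weaker: Protocol 15.1.25 and the censoring text of SAP 2.8.1 place the assessment before the censoring reason or the new therapy. It does nothing for case A.

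**Scans may stop at new therapy.** Protocol 7.1.5.3 moves such patients to survival follow-up, and Protocol 15.1.39 mentions reason 4 for patients not followed for progression after treatment. Yet Protocol 7.1.5.2 continues scans until PD, "withdrawal of consent from tumor assessment, lost to follow-up or death", with no mention of new therapy. The point is unsettled. If scans do stop, the supportive analysis changes nothing for A and B.

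**The consequence is small.** This stands in part. PFS is a descriptive secondary endpoint, no PFS date or estimate changes, the trigger is discretionary, and by-patient listings in a 20-patient study would let a reader spot a misallocation. The rates for q are assumptions. A plan that sets out to give an exact rule for programming should still give the right one.

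**Conclusion.** The concern holds. As written, the reason 5 line contradicts Protocol 15.1.39 and departs from its companion rules for reasons 1 to 3, with no deviation declared. Case A is miscoded on any reading that follows the stated formula. Case B is miscoded when LATA is taken before the new therapy, the better-supported reading.

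The reported table of censoring reasons would be wrong, and the trigger count would be correct or too low, never too high. One miscoded patient is enough to miss the trigger at a true count of 5, and two at a true count of 6. The probabilities rest on assumed q and only show a range. If fewer than 5 patients are truly censored for new therapy, the trigger is not met under either rule. Whether a missed trigger hides a change for patients like A and B depends on scans continuing after new therapy. Main PFS results are unaffected. This should be corrected, but it does not threaten the primary conclusions.

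**What to change.** Replace the reason 5 line with: else if min date equals the start date of further anti-neoplastic therapy, and that start date minus the LATA date is at most D2, then PFS censoring reason = 5. State that LATA here is the last adequate assessment before that start date. Base the 25% trigger on the corrected count, or run the supportive PFS analysis regardless of the count.

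The cost is one programming line and at most one extra Kaplan-Meier table.

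### SAP 4.7.1: a patient lost during off-treatment tumor follow-up, within 18 weeks of the last adequate scan, cannot be given the PFS censoring reason 'Lost to follow-up'

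*SAP*

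**What the plan says.** SAP 2.8.1 plans a summary of PFS censoring reasons, and SAP 4.7.1 gives an ordered list of rules to derive them. Reason 2 (lost to follow-up) has three conditions:

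- the minimum date equals the date of treatment discontinuation;
- that date is no more than D2 after the last adequate tumor assessment (LATA);
- loss to follow-up is the "date of discontinuation reason in the [End of Treatment Phase Disposition] eCRF page".

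No other rule produces reason 2. A patient who matches no rule gets the default: "Else PFS censoring reason = 4", which is adequate assessment no longer available. The minimum date is the earliest of the analysis cut-off, the start of further antineoplastic therapy, and "date of withdrawal of consent, date of discontinuation due to loss to follow-up". No eCRF page is named for the last of these.

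Protocol 7.1.5.2 keeps patients who stop treatment without progression in 8-weekly tumor follow-up and gives a different page for what happens next: "Once the patient ceases tumor follow-up, the reason for completion should be recorded on the End of Post Treatment Phase Disposition eCRF page". Protocol 15.1.31 lists loss to follow-up among the reasons for completing that phase. Protocol 15.1.39 says that censoring reasons are calculated "based on the treatment completion page, the study evaluation completion page and the survival page".

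**The concern.** There are two ways to be lost in this trial: while on LDK378, or later, off treatment and still being scanned. The reason 2 rule covers only the first. For a patient lost by the second route, the End of Treatment page already holds another reason, such as an adverse event or patient decision, so the third condition cannot be met. The first condition fails too, because the loss comes after the treatment discontinuation date.

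The censoring-reason summary is there to tell the reader why PFS follow-up ended. A loss after stopping treatment without progression may be informative, and it should appear in the loss row when the protocol's definition puts it there.

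**Working it through.** **Inputs (SAP 4.7.1).** The interval: "the protocol defined schedule of tumor assessment is every 8 weeks". The window: "each assessment is expected to be performed at the scheduled time point plus or minus 1 week, i.e., the window is 2 weeks". The SAP states that D2 "will be used to determine the PFS censoring reason".

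**The plan's own figure.** D2 = 2 × 8 + 2 = 18 weeks, as the SAP states.

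**Trace.** Take a patient with a baseline scan, no PFS event, no new therapy and no withdrawal of consent. Treatment stops at week 20 for an adverse event, LATA is at week 24, the loss is recorded on the End of Post Treatment page at week 34, and the cut-off is at week 60.

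1. The rules for no baseline scan, new therapy, an event after two or more missed assessments, and consent withdrawal do not apply.
2. Minimum date = min(60, 34) = 34.
3. Reason 2: week 34 is not week 20, and the End of Treatment reason is not loss. It fails.
4. Reason 1 (ongoing without event): week 34 is not week 60. It fails.
5. The default gives reason 4.

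Under protocol 15.1.39, reason 4 takes precedence over a loss only when the loss comes more than the specified period after the last adequate assessment. Taking that period as D2, the gap is 34 − 24 = 10 weeks, which is within 18. The protocol label is therefore lost to follow-up.

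**Varying the loss date** (LATA week 24, cut-off week 60):

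| Loss recorded | Gap from LATA | SAP rule | Protocol 15.1.39 |
|---|---|---|---|
| Week 34 | 10 weeks | 4 | lost to follow-up |
| Week 42 | 18 weeks | 4 | lost to follow-up |
| Week 43 | 19 weeks | 4 | 4 |
| Week 50 | 26 weeks | 4 | 4 |

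**Control.** A patient lost on treatment at week 32 with LATA at week 24 (gap 8 weeks) gets reason 2, as intended.

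**Alternative programming of the minimum date.** Suppose the off-treatment loss date were left out. The minimum date would then be the cut-off. With LATA at week 24, a cut-off at week 40 or 42 (gap 16 or 18 weeks) gives reason 1, and a cut-off at week 43 (gap 19 weeks) gives reason 4. Over a grid of LATA, loss and cut-off dates, reason 2 was never returned under either way of forming the minimum date.

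**Size.** One patient is 1/20 = 5% of the planned FAS.

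**The case against.** The best defence is that the slip is small and that several larger conclusions do not follow from it. Four such conclusions are tempting.

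- *Every off-treatment loss is mislabelled.* It is not. Protocol 15.1.39 itself prefers reason 4 once the loss is more than the specified period after the last adequate assessment. Protocol 7.1.5.4 requires due diligence before a patient is declared lost, so some losses may well pass 18 weeks, where the SAP label is correct.
- *Lost patients will be reported as ongoing.* This needs the minimum date to be restricted to the End of Treatment page, and the SAP states no such restriction. SAP 4.3 reads discontinuation dates from both disposition pages for last contact, which favours including the off-treatment loss date. The result is then reason 4.
- *The losses are hidden.* SAP 2.5 tabulates the reasons for leaving post-treatment efficacy follow-up from the End of Post Treatment page and lists disposition by patient. The gap analysis in SAP 2.8.1 also takes study termination dates into account.
- *SAP Section 3 conceals a change to a protocol analysis.* Protocol 10.5.2 leaves the detail of the censoring rules to the analysis plan, protocol 15.1.28 presents its contents as guidance, and 15.1.39 lists source pages without matching pages to reasons. An incomplete implementation is a fairer description.

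All four limits stand. None of them makes reason 2 reachable for a loss inside 18 weeks. There the SAP and 15.1.39 give different labels, and one study report could show a patient as lost in the disposition table but not in the PFS censoring table.

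**Conclusion.** The rule is wrong as written, within narrow bounds. It mislabels a patient who stops LDK378 without progression, is lost during post-treatment tumor follow-up no more than 18 weeks after the last adequate assessment, and has no event or other censoring reason. That patient gets reason 4 instead of reason 2.

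The effect is 5 percentage points of N=20 per patient, in one descriptive summary. The documents give no loss rate for this phase, so the count is unknown and may be zero. The 10.2% discontinuing for adverse events in CLDK378X2101 (10.2% × 20 ≈ 2 patients) describes treatment discontinuation in another study and cannot stand in for it.

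A reader might infer that PFS itself is biased. The documents do not support that: the patient is censored at the last adequate assessment under either label, so PFS times and Kaplan-Meier estimates are the same. The 25% trigger for the supportive PFS analysis counts patients censored for new anticancer therapy and is also untouched.

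Two assumptions carry the conclusion. The specified period in 15.1.39 is taken as D2, as the SAP does. The study evaluation completion page named there is taken as the End of Post Treatment Phase Disposition page, which protocol 7.1.3 labels study phase completion.

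**What to change.** Reword the reason 2 rule: if the minimum date is the date of discontinuation due to loss to follow-up, taken from the End of Treatment or the End of Post Treatment Phase Disposition page, and that date minus the LATA date is at most D2, then the reason is 2. State in the minimum-date definition that both pages are used, which also closes the route to reason 1.

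With this wording and LATA at week 24, losses at weeks 34 and 42 become reason 2, and a loss at week 43 stays reason 4, as 15.1.39 requires.

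The cost is one line of SAP text, a clarifying phrase and the matching line of program. Both pages are already collected.
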